2.2 Secondary Objectives (or Aim)

The secondary objective is to evaluate preliminary efficacy of DECIDES using a randomized trial.

Hyp 2a. AYA randomized to DECIDES and DECIDES + coach will report greater involvement in and shared decision-making than AYA assigned to Usual Care.

Hyp 2b. AYA and caregiver(s) randomized to DECIDES and DECIDES + coach will report more positive decision-making processes (greater knowledge of their cancer and clinical trials, more balanced attitudes toward clinical trials, and more decision certainty, satisfaction and self-efficacy) compared with those assigned to Usual Care.

Hyp 2c. For DECIDES and DECIDES + coach participants who are offered enrollment on a clinical trial, the enrollment decision (yes/no) will align with AYA values.

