3.3 Study Population

The study will include:

- AYA (ages 15-24 years) newly diagnosed or relapsed with cancer that are receiving treatment for a leukemia/lymphoma, solid tumor, or brain tumor in the Division of Oncology of the Children's Hospital of Philadelphia, and their caregiver(s) (primary and secondary, if applicable). AYA that are 18 and older may participate without a caregiver.
- Oncology health care providers that participate in decision-making about cancer treatment with enrolled AYA and caregiver(s).

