3.3.1 Inclusion Criteria

AYA

- 1) Ages 15-24 years old.
- 2) Newly diagnosed or relapsed with a leukemia/lymphoma, solid tumor, or brain tumor within six weeks of study enrollment.
- 3) Ability to read and speak English.
- 4) If <18 Years Old: Parental/guardian permission to participate (informed consent).

CAREGIVER

- 1) Parent or Legal Guardian of a participating AYA.
- 2) Ability to read and speak English.

ONCOLOGY HEALTH CARE PROVIDER

- 1) Oncology health care provider involved in decision-making about cancer treatment with enrolled AYA patients and caregiver(s).
- 2) Ability to read and speak English.

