5 STUDY EVALUATIONS AND MEASUREMENTS

5.1 Electronic Health Record Review

Medical information will be abstracted from the AYA patients' electronic health record (EPIC) for the following purposes:

- Enrollment Decision
- Demographics
- Diagnosis, date of diagnosis, age at diagnosis
- Intensity and types of treatments received (Using the Intensity of Treatment Rating-III)

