6.2 Secondary Endpoints

The secondary objective is to evaluate preliminary efficacy of DECIDES using a randomized trial.

Hyp 2a and Hyp 2b. Because all measures are continuous, the primary analyses will be summarizing mean and 95% CI by groups and two-sample t test comparing groups for the post-intervention outcome measures. With the sample size of 20 family units for each DECIDES group and 10 family units for usual care, we will have 80% power to detect an effect size of 1.26 (that is, mean difference between the two groups is 1.26 x Standard Deviation).

Hyp 2c. Each AYA and caregiver will have two value scores: Σ factors endorsed as supporting enrollment/ Σ factors endorsed as not supporting enrollment. Consistency of value to enrollment decision will be evaluated with Tetrachoric correlation with 95% CI.

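### Hyp 2c records no enrollment decision date, so choices that DECIDES could not have informed are pooled with those it could; its tetrachoric correlation also needs a cut of the value score that the plan does not state

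*Combined protocol and SAP*

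**What the plan says.** The secondary objective, in sections 2.2 and 6.2, is to "evaluate preliminary efficacy of DECIDES using a randomized trial". Hyp 2c sits under it and reads: "For DECIDES and DECIDES + coach participants who are offered enrollment on a clinical trial, the enrollment decision (yes/no) will align with AYA values". It sets no condition on when the decision was made.

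For the analysis, section 6.2 says "Each AYA and caregiver will have two value scores", one summing the factors that support enrollment and one summing those that do not. It then says "Consistency of value to enrollment decision will be evaluated with Tetrachoric correlation with 95% CI". It names no instrument, time point, rule for combining the two sums, or cut.

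The decision comes from the chart review in section 5.1, which lists it only as "Enrollment Decision". The same list does ask for a date elsewhere: "Diagnosis, date of diagnosis, age at diagnosis".

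The entry criterion in section 3.3.1 is "Newly diagnosed or relapsed with a leukemia/lymphoma, solid tumor, or brain tumor within six weeks of study enrollment". Neither the inclusion nor the exclusion criteria require a pending treatment or trial decision. Randomization follows the baseline assessment (section 3.1.2), and the post-intervention assessment (T2) comes about six weeks after randomization (section 3.1.3).

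**The concern.** DECIDES can help align a decision with values only if it is used before the decision. The background (section 1) says families have little time to decide, and it presents the study as a test in live rather than retrospective decisions. Entry can nevertheless come weeks after diagnosis, and randomization and first website access come later still. Nothing in the plan keeps out, or even identifies, a choice already made by then.

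Without the date, a high Hyp 2c correlation could be read as support for DECIDES when part of it comes from families who chose before they saw it. A low one could hide good alignment among those who used it in time.

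The statistic raises a separate issue. Enrollment is yes or no, but the value scores are sums. A tetrachoric correlation can be computed only after those sums are reduced to two categories. If the rule is chosen after the data are seen, the estimate depends on that choice, and any cut discards information in an already small sample.

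**Working it through.** The plan states no sample size, expected correlation or interval width for Hyp 2c, so there is no figure to reproduce. The calculations below use inputs that are not in the documents: 70% of those offered a trial enroll, and the value score is normal. They illustrate and do not predict.

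**1. Can an early decision enter?** Set side by side, section 2.2 takes every DECIDES-arm participant offered a trial, section 5.1 gives the decision without a date, and section 3.3.1 allows entry up to six weeks after diagnosis or relapse. Section 6.1 summarizes click behavior and time to DECIDES implementation, but only to describe feasibility, and does not link them to the decision. So an early decision is included and cannot be recognized from the listed fields.

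**2. Sample.** The target is 20 + 20 = 40 AYA in the two DECIDES arms (section 3.1). If all 65 family units enroll at 1:2:2 (section 8.1.1), it is 65 × 4/5 = 52. Fewer will be offered a trial; the share is not given.

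**3. Effect of pooling.** Let w be the share of early decisions, with the same score distribution and enrollment rate in both groups. The covariance of score and decision averages over the groups, so for the biserial correlation

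ρ_pooled = (1 − w) × ρ_later + w × ρ_earlier.

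| w | later 0.6, earlier 0 | later 0, earlier 0.6 |
|---|---|---|
| 0.25 | 0.75 × 0.6 = 0.45 | 0.25 × 0.6 = 0.15 |
| 0.50 | 0.5 × 0.6 = 0.30 | 0.5 × 0.6 = 0.30 |
| 0.75 | 0.25 × 0.6 = 0.15 | 0.75 × 0.6 = 0.45 |

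At w = 0.5 the two opposite situations give the same answer. The tetrachoric cannot separate them either, because the pooled 2×2 table is identical.

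**4. Values measured after the choice.** Suppose the score is taken at T2, that prior values were unrelated to the decision, and that each person's score then moved d SD toward the choice made. With p = 0.7, q = 0.3, pq = 0.21 and φ(z) = 0.3477:

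r_pb = 2d√(pq) / √(1 + 4d²pq), and biserial = r_pb × √(pq)/φ(z) = r_pb × 1.318.

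For d = 0.25, r_pb = 0.2291/1.0259 = 0.223, giving a biserial of 0.29. For d = 0.5 and 0.75 it is 0.55 and 0.75. Changing the statistic does not cure a timing problem, so the time point of the score must be stated.

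**5. Empty cells under the tetrachoric.** Assume 70% in the upper category of both variables. At a true correlation of 0.5 the cell probabilities are 0.557, 0.143, 0.143 and 0.157. At n = 15 the chance of at least one empty cell is 2(0.857)^15 + (0.843)^15 minus overlaps = 0.275 − 0.016 = 0.26. Over correlations of 0.5 to 0.8 the range is 26–46% at n = 15, 12–30% at n = 20 and 0.5–5% at n = 40.

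**6. Precision of an uncut score (simulation, same 70/30 cut for the tetrachoric).** SD of the estimate at a true 0.6:

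| n | biserial | tetrachoric | reduction |
|---|---|---|---|
| 10 | 0.341 | 0.348 | 2% |
| 15 | 0.271 | 0.318 | 15% |
| 20 | 0.238 | 0.287 | 17% |
| 40 | 0.159 | 0.207 | 23% |

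The median 95% interval at a true 0.6 is 0.09 to 0.86 (biserial) against −0.08 to 0.94 (tetrachoric) at n = 20, and 0.26 to 0.81 against 0.13 to 0.88 at n = 40. Coverage of the profile-likelihood interval is 0.909 against 0.923 at n = 20, and 0.928 against 0.936 at n = 40, so the biserial's shorter interval comes with slightly lower coverage.

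**The case against.** The strongest reply is that Hyp 2c claims only that decisions align with values in the DECIDES arms. It has no comparator and no test; the randomized comparisons are Hyp 2a and 2b. Taken as one descriptive estimate with an interval, it does not claim that DECIDES caused the alignment. That is right, and it limits the point. But the analysis is filed under preliminary efficacy, and a description of alignment is more useful when it distinguishes decisions the tool could have reached.

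A reader might infer that many decisions will already be closed at entry, because section 3.3 describes the population as "newly diagnosed or relapsed with cancer that are receiving treatment for a leukemia/lymphoma, solid tumor, or brain tumor". The documents do not support that: the phrase also serves to say where care is given, and the background stresses real-time decisions. Early decisions are possible and unidentified; their frequency is unknown.

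The Hyp 1b interviews in both DECIDES arms are meant to cover timing and the decision process (sections 2.1 and 5.3), so the order of events may be partly known. They give qualitative recall, not a recorded date that Hyp 2c would use.

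A reader might also infer that the tetrachoric correlation is invalid here. It is not. With a split fixed in advance, such as supporting sum larger than opposing sum, it is a defensible choice. What is missing is the rule.

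Finally, the source of the scores is uncertain. Table 1 appears to pair alignment with the PRPQ at T2, but that row is broken in the available text, and the value clarification exercise (sections 1.1.3 and 4.1.3) is another possible source. If it is the source, the illustration about T2 may not apply; the date point is unaffected.

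**Conclusion.** The point holds in this form. As written, Hyp 2c pools enrollment decisions whatever their order relative to randomization and first DECIDES access, and the listed data cannot separate them. This rests on the text alone. The size of the effect cannot be computed; the 0.30, 0.45 and 0.15 results and the T2 shift of 0.29 to 0.75 depend on assumed inputs and show only what could happen.

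Second in importance, the tetrachoric correlation implies a cut that section 6.2 does not state. Keeping the score uncut lowers the SD of the estimate by 11–23% at n = 15 to 40 (true correlation 0.5 to 0.7, assumptions as above), with little or no gain at n = 10.

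Two stronger conclusions are not supported. The gap does not undermine the randomized comparisons in Hyp 2a and 2b, which do not use the enrollment decision. Nor does it show that the primary feasibility objective fails: the planned usage measures remain valid, and the order of access and decision would be a useful addition to them. The matter is worth correcting because it is cheap and changes what Hyp 2c can say, but it concerns a non-comparative secondary analysis in a pilot.

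**What to change.** 1. Add the enrollment decision date to the chart abstraction in section 5.1.
2. Base Hyp 2c on decisions dated after first DECIDES access, taken from the usage analytics. List separately the decisions made before randomization and those made between randomization and first access. State in advance how same-day cases and families who never open the site are handled.
3. As an added feasibility description, report the share of DECIDES families whose first access came before the decision.
4. Describe Hyp 2c in sections 2.2 and 6.2 as non-comparative concordance, not evidence of efficacy.
5. In section 6.2, name the score source (PRPQ or value clarification exercise) and its time point. Preferably use a biserial correlation, with a profile-likelihood 95% CI, on the uncut supporting-minus-opposing score. Keeping the tetrachoric with a pre-stated split (supporting sum larger than opposing sum) is an acceptable alternative.

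The cost is one chart field, some wording, and a smaller Hyp 2c sample. If 20 AYA were offered a trial and half decided too early (assumed), n = 10. The median 95% interval at a true 0.6 would then be −0.08 to 0.93, and the biserial would have almost no precision advantage. Its interval is approximate in small samples (simulated coverage 87–92% at n = 10 to 20), and it assumes a roughly normal score. It cannot be computed if everyone chooses the same way, which at 70% enrollment has probability 0.7^10 + 0.3^10 = 2.8% at n = 10; raw counts should be given in that case.

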6 STATISTICAL CONSIDERATIONS

Demographic characteristics and all measurements will be summarized.

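### Hyp 2c predicts that enrollment decisions align with AYA values, but its only planned statistic, a tetrachoric correlation, measures association and can be high when most AYA with opposing values enrolled

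*Combined protocol and SAP*

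**What the plan says.** Section 2.2 limits Hyp 2c to DECIDES and DECIDES + coach participants who are offered a clinical trial, and predicts that "the enrollment decision (yes/no) will align with AYA values".

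Section 6.2 builds the value side from counts of endorsed factors: "Each AYA and caregiver will have two value scores: Σ factors endorsed as supporting enrollment/ Σ factors endorsed as not supporting enrollment". It gives no rule for turning the two scores into the binary variable that a tetrachoric table needs, and none for equal scores. The analysis is then a single sentence: "Consistency of value to enrollment decision will be evaluated with Tetrachoric correlation with 95% CI".

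No proportion aligned, kappa, rule for empty cells or threshold for calling decisions aligned is specified. The opening of section 6 says "Demographic characteristics and all measurements will be summarized", which does not commit to any agreement measure.

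**The concern.** Alignment is a statement about each person: did this AYA's decision match this AYA's values? A tetrachoric correlation answers a different question, namely whether AYA with more favourable values tend to enroll more often than the others. It assumes a latent normal variable behind each binary one and sets both cut-points from the margins. If nearly everyone enrolls, the enrollment cut-point moves and the coefficient need not fall.

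The group of most interest for a decision aid is AYA whose values oppose enrollment but who enroll. The planned statistic does not show how large that group is, and a high value could be read as good alignment when most of that group enrolled.

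**Working it through.** **Inputs.** From section 2.2: the target is alignment, among AYA in the two DECIDES arms who are offered a trial. From section 6.2: "With the sample size of 20 family units for each DECIDES group and 10 family units for usual care", so about 20 + 20 = 40 AYA at the planned size, and fewer if some are not offered a trial. The offer rate, enrollment rate and share with favourable values are not stated, so the tables and rates below are assumptions. The plan gives no figure for Hyp 2c to reproduce; its power statement concerns Hyp 2a and 2b.

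Tables are written as (support and enrolled, support and declined, oppose and enrolled, oppose and declined).

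**Example 1: (10, 0, 6, 4), n = 20.**
- Margins: 10/20 = 0.50 support, 16/20 = 0.80 enrolled.
- At rho = 1 both binary variables come from one latent variable. The fitted cells are min(0.50, 0.80) = 0.50, then 0, then 0.80 - 0.50 = 0.30, then 1 - 0.80 = 0.20. Times 20 this is 10, 0, 6, 4: an exact fit, so the maximum-likelihood estimate is 1.0, on the boundary.
- With 0.5 added to the empty cell the estimate is about 0.72; with 0.5 added to all cells, about 0.73.
- Decisions matching values: (10 + 4)/20 = 70%, exact 95% CI about 46-88%. Opposed AYA enrolled: 6/10 = 60%.
- Chance match: 0.50 x 0.80 + 0.50 x 0.20 = 0.50, so kappa = (0.70 - 0.50)/(1 - 0.50) = 0.40.

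**Example 2: (23, 1, 10, 6), n = 40, no empty cell.** The estimate is 0.72. Matching is 29/40 = 72.5%, and 10/16 = 62.5% of opposed AYA enrolled. The mismatch is therefore not only an effect of empty cells.

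**It is not only a small-sample effect.** At a true rho of 1 with more enrolling than supporting, the proportion enrolled among opposed AYA is (P(enroll) - P(support))/(1 - P(support)). With 0.875 and 0.50 this is 0.375/0.50 = 75%.

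**The reverse error.** For (36, 2, 2, 0), 36/40 = 90% of decisions match, but the uncorrected estimate lies at the -1 boundary.

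**How often.** Bivariate-normal simulation with 70% holding values in favour and latent correlation 0.7. The event counted is the specific harm: no supporter declines, at least one opposed AYA declines, and more opposed AYA enroll than decline.

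| Assumed enrollment | n = 40 | n = 20 | n = 12 |
|---|---|---|---|
| 50-70% | at most about 0.1% | at most about 2% | at most about 4% |
| 80% | about 5% | about 13% | about 15% |
| 90% | about 43% | about 46% | about 32% |

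**The planned interval.** With cut-points held at the margins, the likelihood-based 95% lower limit is about 0.28 in Example 1, and the interval in Example 2 is about 0.24 to 0.93.

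**The case against.** Four points can be made for the plan.

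- **Uncertainty would show.** The plan asks for a 95% CI, and with so few AYA it would be wide; neither example's interval would read as near-perfect alignment. This limits the practical harm. But the interval is for association, so it does not tell the reader how many decisions matched values.
- **A value of exactly 1.0 depends on software.** That is so: a continuity correction brings Example 1 to about 0.72. The plan names no correction, and the corrected value is still not a measure of agreement.
- **The stakes are modest.** Hyp 2c is one secondary hypothesis under preliminary efficacy, the primary aim is acceptability and feasibility, and no threshold or decision hangs on the coefficient. This stands, and it argues for a recommended change rather than an essential one.
- **Overall percent match has its own flaw.** If 90% hold values in favour and 90% enroll independently of values, 0.9 x 0.9 + 0.1 x 0.1 = 82% match by chance. This stands, and the fix has to allow for it.

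A reader might also infer that a falsely perfect coefficient is likely here. Under the same assumptions, the chance of any empty cell is indeed larger: about 10%, 37% and 64% at 80% enrollment and 51%, 75% and 89% at 90% (n = 40, 20, 12). Those figures include tables in which no opposed AYA enrolled, which is a good result, and tables with an empty margin, where the coefficient cannot be estimated. Nor do the documents support assuming that nearly all will enroll. The background in section 1 reports lower AYA enrollment when a trial is offered, although it also describes young patients as motivated to take part in research.

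**Conclusion.** The point holds as a mismatch between hypothesis and statistic: Hyp 2c is about agreement, the only specified analysis measures association, and nothing else in the plan supplies an agreement measure. That conclusion needs no assumption about rates.

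The size of the practical risk does. The extreme outcome, a coefficient of 1.0 with most opposed AYA enrolled, ranges from negligible at 50-70% enrollment to between about 32% and 46% at 90%, given 70% with values in favour, a latent correlation of 0.7, 12 to 40 AYA and no continuity correction. The documents allow no choice within that range, so the outcome should be described as possible, not expected. The change should be made, but it does not threaten the trial's primary aim.

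**What to change.** In section 6.2, replace the Hyp 2c analysis sentence with text to this effect:

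1. Classify each AYA by the sign of the net value score (factors supporting minus factors not supporting enrollment). State the rule for ties in advance, for example showing them as a separate group left out of the match proportion.
2. Report the 2x2 table and, with exact 95% CIs, the proportion enrolled among AYA with net values for enrollment, the proportion enrolled among those with net values against, and the overall proportion of decisions matching values.
3. Interpret the overall match only beside the within-group proportions or a chance-corrected measure such as kappa.
4. Keep the tetrachoric correlation as descriptive only, if at all.

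The cost is a few sentences. The value scores are already planned, and the enrollment decision is already abstracted from the health record (section 5.1), so no new data are needed. The downside is that the exact intervals are wide (14/20 gives about 46-88%) and the result may look less favourable than a correlation.

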7 SAFETY MANAGEMENT

7.1 Clinical Adverse Events

Clinical adverse events (AEs) will be monitored throughout the study.

7.2 Adverse Event Reporting

Since the study procedures are not greater than minimal risk, Significant Adverse Events (SAEs) are not expected. If any unanticipated problems related to the research involving risks to subjects or others happen during the course of this study (including SAEs) they will be reported to the IRB in accordance with CHOP IRB SOP 408: Unanticipated Problems Involving Risks to Subjects. Adverse Events (AEs) that are not serious but that are notable and could involve risks to subjects will be summarized in narrative or other format and submitted to the IRB at the time of continuing review.

8 STUDY ADMINISTRATION

8.1 Treatment Assignment Methods

8.1.1 Randomization

We will enroll up to 65 family units to achieve 50 evaluable family units that are randomized to three groups with a 1:2:2 ratio for usual care, DECIDES, and DECIDES +

coach. The randomization will be stratified by two age categories, under 18 years old and 18 years or older, and we expect 50% of the AYA patients in each of the two strata. For each stratum, we use a blocked randomization of block size of 5. The statistician will generate the randomization sheet for assigning patients into intervention groups.

8.2 Data Collection and Management

The data collection and management plan is consistent with CHOP Policy A-3-6: Acceptable Use of Technology Resources that defines the requirements for encryption and security of computer systems.

- Identifiable data will be collected as part of this study. This data includes full names/initials, dates of birth, addresses, telephone numbers, and e-mail addresses. However, participants will be identified by alphanumeric code only. This precautionary step allows for the electronic transfer of data without using data encryption techniques. At each stage of data collection and maintenance, measures are taken to ensure that all identifying information is taken out of data archives, and any hard copies of data that could identify participants are stored in locked file cabinets with restricted access, and that data files are password protected. Participant identification numbers are used that do not reveal the identity of participants (e.g., no use of birth dates, initials, social security numbers, etc.). Identifiable data will be stored in a locked cabinet at one of the research buildings at CHOP, and only members of the research team will have access to the data. If the results of this study are presented at scientific meetings or published in professional journals, they will not contain information that could be used to identify patients, parents, or family members.
- Electronic survey data will be collected and stored using REDCap (Research Electronic Data Capture) database, a secure web-based software database supporting clinical and translational research databases. The database will be password-protected, stored, and backed up on a daily basis by CHOP's Research Institute. REDCap provides data management functionality; including automated export procedures for seamless data downloads to Excel and commonly used statistical packages (SPSS, SAS, Stata, R). The database will incorporate range checks and between-variables consistency checks to ensure quality control. The system will signal the presence of questionable or potentially incorrect items. After data cleaning and quality assurance procedures are completed, pertinent sets of data will be exported into SPSS for statistical analysis.
- Electronic interview data will be collected and audio and/or video-recorded using Microsoft Teams (Office 365), CHOP's preferred HIPAA compliant video conference platform. Microsoft Teams utilizes 2-factor authentication, data encryption, and restriction on anonymous users joining a meeting, making it an appropriate application to facilitate sensitive video conversations and protect PHI. This application will be utilized to connect the study team personnel with study participants during the semi-structured qualitative interview. Microsoft Teams provides an interoperable cloud-based video meetings service that connects multiple users across different devices and platforms. Every Microsoft Teams member on the study team has a private "meeting room" in the Microsoft Teams cloud to schedule and host video meetings. In the event

that participants experience WIFI connectivity issues during the interview, Microsoft Teams provides a telephone number that participants can call directly into the Microsoft Teams private “meeting room” using their phone, as needed.

- Interview recordings (audio and/or video recordings containing participant identifiers) will be transferred from Microsoft Teams to a CHOP password-protected desktop computer on the Principal Investigator’s shared drive through a secure upload. The study team will use a CHOP-approved vendor for professional transcription services (that has a BAA with CHOP in place). Transcribed interview data will be stored on a CHOP password-protected desktop computer, on the Principal Investigator’s shared drive, and loaded into ATLAS.ti© software to facilitate data organization and content analysis. After all analyses are complete, the files will be destroyed, and personal identifiers will not be retained with the data. All computerized study databases for questionnaire data will be kept on a secure Windows NT server located at one of the hospital’s research buildings. This server is also protected by a firewall to reduce the risk of unauthorized access to study information.

